## 5 Analysis Populations

### 5.1 Intention-to-Treat Population

The Intention-to-Treat (ITT) Population will include all subjects who are randomized and will be analyzed according to the randomization scheme. Subjects will be analyzed according to the treatment they are planned to receive according to the randomization schedule. The ITT Population is the primary population for the analysis of effectiveness parameters.

### 5.2 Per-Protocol Population

The Per-Protocol (PP) Population will include all subjects in the ITT Population who complete the primary endpoint assessment at 3 months after baseline or last treatment without any deviations considered to have substantial impact on the primary effectiveness. Subjects will be analyzed according to the treatment they are planned to receive according to the randomization schedule. A sensitivity analysis of the primary effectiveness endpoint will be performed based on the PP Population.

### 5.3 Safety Population

The Safety Population will include all subjects who were treated with Restylane Lyft with Lidocaine or Juvéderm Voluma XC, and will be analyzed according to the as-treated principle. Subjects will be analyzed according to the treatment they have received according to the actual treatment. Safety analysis will be performed based on the Safety Population set.

## 6 Subject Disposition

Subject disposition will be summarized in a table. The number of screened, randomized, treated, completed, and withdrawn subjects will be presented, as well as number and percentages of subjects in each analysis population (ITT, Per-Protocol and Safety Populations). Percentages for the number of screen failures and randomized subjects are based on the number of subjects screened. Percentages for the number of subjects treated, the number of subjects who completed the study, the number of subjects who did not complete the study, and the number of subjects in the PP Population are based on the number of subjects in the ITT Population. The numbers and percentages of subjects associated with withdrawal reasons will be presented, with percentages based on the number of withdrawn subjects per treatment. A subject disposition table by study site will also be presented, with the same parameters reported.

Galderma

Protocol number: 43USCH2208

Protocol V4.0

Subject accountability will be summarized by visit with the following:

- Number of subjects expected at each visit.
- Number of subjects who performed each visit.
- Number of subjects who missed each visit.
- Number of subjects withdrawn at each visit.

Subjects who were excluded from the study will be presented in a data listing, along with reasons for exclusion. All subjects' completion and discontinuation information will be presented in a data listing that will report the last visit performed with date, the date of completion or discontinuation and the reason for discontinuation.

A study visit listing will include the reason for missing the study visit and how the remote visit was conducted when it applies. For unscheduled visits, changes since last visit concerning adverse events, concomitant medications or procedures will also be displayed.

An informed consent and randomization data listing will include the date and version of the initial consent and information on re-consent if it applies, as well as the date and time of randomization and the assigned treatment.

## 7 Protocol Deviations

A protocol deviation occurs when a subject deviates from the protocol procedures. Depending on the seriousness of the deviation, the subject might be excluded from the PP analysis. Since the PP Population will be used as a sensitivity analysis for the primary analysis at 3 months after last treatment only, the focus will be on deviations occurring before and on the 3 months after last treatment visit day, as they might compromise the primary endpoint. For this study, the protocol deviations that will exclude subjects from the PP Population are identified (but not limited to) in Table 6 below.

**Table 7. Protocol deviations**

| Deviation   |
|---|
| Any subject that conducts their 3 months after last treatment visit out of window by greater than 21 days or earlier than 7 days                            |
| Any subject not treated according to the assigned treatment.  |
| Any subject that does not have a Blinded Evaluator GCRS onsite live assessment at the primary endpoint visit (3 months after last treatment).               |
| Any subject that does not have an available Baseline (or screening if combined) Blinded Evaluator GCRS onsite live assessment.                              |
| Any subject that does not have grade 1 or 2 on either the Blinded Evaluator or Treating Investigator GCRS onsite live assessment at screening and Baseline. |

Galderma

Protocol number: 43USCH2208

Protocol V4.0

| Deviation  |
|--|
| Any subject with prohibited concomitant treatments/procedures prior to the 3 months after last treatment visit considered to have a substantial impact on the primary efficacy outcome.  |
| Any subject with a prohibited medical history, unstable medical history condition, or medical history condition that worsens prior to the 3 months after last treatment visit considered to have a substantial impact on the primary efficacy outcome. |

Protocol deviations will be presented descriptively. The number and percentage of subjects who have protocol deviations, the total number of deviations and the type of protocol deviation will be summarized using the ITT Population. The above summary of protocol deviations will be repeated by site as well. Protocol deviation listings will be reviewed, and each subject will be classified as belonging to the per-protocol set or not. Exclusions from the PP Population will be identified and documented prior to database lock.

Protocol deviations will be presented in a data listing that will display the visit where the deviation was reported, the date where the deviation occurred, the deviation type and description, the action taken, if it was reported to the Institutional Review Board (IRB) and if the deviation was due to COVID-19. Subjects who are excluded from the PP Population will also be presented in a data listing, along with their reason(s) for exclusion.

## 7.1 Out of Window Visit Duration

When a subject performs a planned study visit outside of the protocol-specified visit windows ([Section 16.2](#)), the subject has an out of window study visit, which is considered a type of protocol deviation for this study. Knowing a subject's Screening visit (Visit 1a) and Baseline visit (Visit 1b) and using the protocol-specified visit windowing, one can calculate a subject's target study visit window date range for each planned study visit. Then, by comparing a subject's actual study visit date to the target study visit window date range, one can calculate the days over/under the actual study visit in relation to the target study visit date, corresponding to the study visit out of window duration.

The duration, in days, a study visit is out of window will be summarized by treatment group, overall, and by visit. Out of window visit durations will also be presented by site. Duration will be split into the following below categories. Duration categories will include both days before and days after the target planned visit date.

- +/- 1-2 days.
- +/- 3-7 days.
- +/- 8-20 days.
- +/- 21 or more days.

The number and percentage of subjects within each out of window duration category will be presented descriptively. For the overall analysis, percentages will be calculated using the number of subjects with an out of window visit at the respective visit as the denominator; for the by site analysis, percentages will be calculated using the number of

Galderma

Protocol number: 43USCH2208

Protocol V4.0

subjects at the respective site with an out of window visit at the respective visit as the denominator.

## 8 Demographic and Baseline Characteristics

### 8.1 Demographic Characteristics

Demographic assessments for this study include:

- Age (years);
- Age Category ( $\leq$  ITT Population median age,  $>$  ITT Population median age);
- Sex at Birth (Male, Female);
- Gender identity (Female, Male, Transgender male-to-female, Transgender female-to-male, Gender nonconforming (neither exclusively male nor female), Other, Decline to answer);
- Ethnicity (Hispanic or Latino, Not Hispanic or Latino);
- Race (White, Black or African American, Asian (Chinese, Asian Indian, Filipino, Japanese, Korean, Vietnamese, Other Asian), American Indian or Alaska Native, Native Hawaiian or Other Pacific Islander, Other);
- Height (cm);
- Weight (kg);
- BMI ( $\text{kg}/\text{m}^2$ );
- Fitzpatrick Skin Type (FST) Score (I, II, III, IV, V, VI);
- Fitzpatrick Skin Type (FST) Cohort at Randomization (I-III, IV, V-VI);
- Baseline GCRS by Blinded Evaluator (0, 1, 2, 3);
- Baseline GCRS by Treating Investigator (0, 1, 2, 3).

Demographic and Baseline characteristics will be summarized using the ITT Population. No formal statistical comparisons between treatment groups will be performed. Continuous variables to be summarized include age (in years), height (in cm), weight (in kg), BMI (in  $\text{kg}/\text{m}^2$ ). Categorical variables include age category, gender, ethnicity, FST, Baseline GCRS by Blinded Evaluator and Baseline GCRS by Treating Investigator.

FST Cohort at Randomization will be used in tables. FST Cohort at Randomization and FST Score will both be included in listings.

Demographic and Baseline characteristics, as well as the childbearing potential and breastfeeding status for female subjects will also be reported in a data listing.

Galderma

Protocol number: 43USCH2208

Protocol V4.0

## 8.2 Medical History

Subjects' medical history will be collected at Screening and at Baseline visits. An event that occurs after the subject signs the Informed Consent Form (ICF) but before enrollment will be recorded in the subject's medical history.

Medical history summaries will be reported using the ITT Population. The number and percentage of subjects reporting medical history and the number of events will be summarized by MedDRA System Organ Class (SOC) and Preferred Term (PT). System Organ Classes and PTs will be sorted in descending frequency first (by Restylane Lyft with Lidocaine group) and then alphabetically if there are ties. Each subject will only be counted once within each SOC and SOC/PT combination. The MedDRA version used will be noted as a footnote in the tables and listings.

Medical history information will also be reported in a data listing presenting the SOC, the PT, the description, and the onset and stop date (or if ongoing).

## 8.3 Dermatological Procedures and Implant History

Subjects' dermatological procedures and implant history will be collected at Screening and at Baseline visits and summarized using the ITT Population in the same way as for subject's medical history ([Section 8.2](#)).

Dermatological procedures and implant history listing will include the SOC, the PT, the procedure or product name, the location and the date.

## 8.4 Concomitant Procedures/Non-Pharmacological Treatments

Concomitant procedures/non-pharmacological treatments are defined as follows:

- Any existing procedures ongoing at the time of the Screening visit.
- Any changes to existing procedures (such as changes in dose or formulation) during the study.
- Any new procedures received by the subject since the Screening visit.

Subjects' concomitant procedures will be collected at all study visits.

Concomitant procedures will be summarized using the ITT Population in the same way as for the medical history. The subset of concomitant procedures administered for treatment-related adverse events (see [Section 10.2.3](#)) will be summarized in the same way in an additional table.

Concomitant procedures listing will include the SOC, the PT, the procedure name, the start and stop date, the reason for procedure, and the related medical history and/or adverse event when it applies.

Galderma

Protocol number: 43USCH2208

Protocol V4.0

## 8.5 Prior and Concomitant Medications

Prior medications are defined as medications that have been used within 30 days preceding the Screening visit or within the timelines specified in the Inclusion/Exclusion criteria, and then stopped prior to the Screening visit. Concomitant medications are any existing medications ongoing at the time of the Screening visit, any changes to existing medications during the study or any new medications received since the Screening visit. Subjects' prior medications will be collected at Screening and concomitant medications will be collected at all study visits.

Prior and concomitant medication summaries will be reported using the ITT Population in two different tables. The number and percentage of subjects reporting prior/concomitant medications and the number of events will be summarized by the WHO Drug Dictionary Anatomical Therapeutic Chemical 4th level (ATC-4) and the Preferred Term (PT). If the 4th level term is not available, the next available level (e.g., Anatomical Therapeutic Chemical 3rd level (ATC-3)) will be used. ATC-4 and PT will be presented by overall descending frequency first, then alphabetically if there are ties. Anatomical Therapeutic Chemical 4th level and PTs will be sorted in descending frequency first (by Restylane Lyft with Lidocaine group) and then alphabetically if there are ties. Each subject will only be counted once within each Anatomical Therapeutic Chemical (ATC) and ATC/PT combination. The subset of concomitant medication administered for treatment-related adverse events (see [Section 10.2.3](#)) will be summarized in the same way in an additional table.

All prior and concomitant medication data for each subject will be included in a data listing that will present the name of the medication, the ATC and PT, the indication, the total daily dose, the route, the start and end date, the reason of administration, and the related medical history and/or adverse event when it applies.

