### 9.1.3 Sensitivity Analysis of Primary Endpoint

To assess the robustness of the primary efficacy results, the following additional sensitivity analyses will be conducted:

- To evaluate the impact of missing data on the primary endpoint, the primary analysis specified in [Section 9.1.2](#) will be repeated using the ITT Population with Observed Cases (OC), that is, no imputation will be done.
- To evaluate the impact of missing data on the primary endpoint, the primary analysis specified in [Section 9.1.2](#) will be repeated using the ITT Population with baseline observation carried forward (BOCF) method.
- To evaluate the impact of missing data on the primary endpoint, the primary analysis specified in [Section 9.1.2](#) will be repeated using the ITT Population with imputation of the worst case. For the GCRS, the worst case is defined as 3 – Severe Retrusion.

Effective date: 2024-05-29 18:37

Effective

Version: 1.0

Galderma

Protocol number: 43USCH2208

Protocol V4.0

- To evaluate the impact of intercurrent events, the primary analysis specified in [Section 9.1.1](#) will be repeated using the ITT Population with MI but excluding subjects that had a prohibited treatment in or near the treatment area prior to 3 months after last treatment. Subjects with prohibited treatments are defined as subjects with a protocol deviation type of “Prohibited medication or procedure” prior to or on their primary endpoint visit.
- To evaluate the impact of intercurrent events, the primary analysis specified in [Section 9.1.1](#) will be repeated using the ITT Population with MI but excluding subjects who were administered treatment not according to randomization. Subjects who were administered treatment not according to randomization are defined as subjects who were randomized but not treated, subjects whose actual treatment at initial treatment or optional touch-up treatment does not match their planned treatment according to the randomization schedule, or subjects who were treated but not randomized.
- To evaluate the impact of intercurrent events, the primary analysis specified in [Section 9.1.1](#) will be repeated using the ITT Population with MI but excluding subjects that used Hyaluronidase prior to 3 months after last treatment.
- A sensitivity analysis of the primary effectiveness endpoint specified in [Section 9.1.2](#) will be performed based on the PP Population with using observed cases.

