### 10.2.3 Relationship to Study Product of Injection Procedure

Each AE will be assessed by the Investigator for a reasonable possibility of a causal relationship with the study product and with its use (the injection procedure), both on a two-point scale (Yes or No). If the response to any of the questions "*Do you consider that there is a reasonable possibility that the event may have been caused by the study product?*" or "*Do you consider that there is a reasonable possibility that the event may have been caused by the study product injection procedure?*" is "Yes", then an AE is considered related for the analysis. Missing relationships will be considered related.

Related AEs will be summarized by SOC, PT and maximum intensity (defined in [Section 10.2.2](#)). Unrelated AEs, as well as serious related AEs, will also each be summarized by SOC, PT and maximum intensity. If a subject has multiple occurrences of the same MedDRA SOC or PT, then only the most severe event will be summarized in the tables for that SOC and PT.

Finally, the number of subjects with related AEs will be summarized by SOC, PT, and action taken (none, medication treatment, non-pharmacological treatment, other procedures/tests, subject withdrawn). Subjects will be only counted in 'None' category if no other action was taken.

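### The two SAP tables of therapy given for treatment-related AEs follow the ITT Population and planned arm, while other safety data follow the Safety Population and actual treatment

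*SAP*

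**What the plan says.** **Parent tables.** For medications, SAP 8.5 states: "Prior and concomitant medication summaries will be reported using the ITT Population in two different tables". For procedures, SAP 8.4 states: "Concomitant procedures will be summarized using the ITT Population in the same way as for the medical history".

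**Subset tables.** SAP 8.5 singles out "The subset of concomitant medication administered for treatment-related adverse events", which "will be summarized in the same way in an additional table". SAP 8.4 makes the same provision for procedures. Both point to SAP 10.2.3 for what counts as treatment-related. Neither changes the population or the arm assignment.

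**Arm assignment.** For ITT, SAP 5.1 says: "Subjects will be analyzed according to the treatment they are planned to receive according to the randomization schedule". For the Safety Population, SAP 5.3 says: "Subjects will be analyzed according to the treatment they have received according to the actual treatment". SAP 5.3 also bases safety analysis on that set. SAP 11.1 places descriptive statistics of all safety data in it, as do Protocol 9.2 and 9.6.

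**Departures from randomisation.** SAP 9.1.1 lists treatment not according to randomisation as an intercurrent event. SAP 9.1.3 spells out three forms: randomised but not treated, given a product other than the planned one at initial treatment or touch-up, and "subjects who were treated but not randomized".

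**Related safety output.** Under SAP 10.2.3, "the number of subjects with related AEs will be summarized by SOC, PT, and action taken". The action categories include medication and non-pharmacological treatment.

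**The concern.** The parent tables describe the background therapy of the randomised population, and ITT suits them. The two subset tables do something else: they show what had to be given because of a reaction judged related to the product or its injection. That is a post-injection safety outcome, although it sits in the SAP's section on demographic and baseline characteristics.

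The related AEs are counted by product received. On the natural reading, the therapies for those same AEs are counted by product planned. Where the two differ, a reader comparing products on the drugs and procedures their reactions required would see some therapy in the wrong column or not at all. The subset tables would also not rest on the same subjects and arms as the related-AE tables.

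**Working it through.** **1. Plan figures used.** The plan gives no figure for this point. The planned arm sizes, 116 and 58 (SAP 3.2.3), serve only as denominators. They follow from the sample size, which reproduces:

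- Control n = (1 + 1/2) × 0.7² × (1.960 + 1.282)² / (0.5 − 0.1)² = 48.3, rounded up to 49.
- Investigational n = 98, so the total is 147, as stated.
- Allowing for 15% dropout, 147 / 0.85 = 172.9, or 173. The planned 174 is the next multiple of 3, as 2:1 allocation needs.

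**2. The rules side by side.**

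| Subject | Subset tables (8.4, 8.5), natural reading | Related-AE tables (10.2.3 under 5.3 and 11.1) |
|---|---|---|
| Randomised, given assigned product | Assigned arm | Same arm |
| Randomised, given the other product | Planned arm | Product received |
| Randomised, never treated | In the denominator; cannot contribute a related AE, since SAP 10.2 analyses only AEs after treatment | Not included |
| Treated, not randomised | Not included (ITT is randomised subjects only) | Product received |

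If everyone falls in the first row, the two approaches give identical tables.

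**3. Weight of one subject.** 1/58 = 1.7 percentage points of the comparator column; 1/116 = 0.9 points of the Restylane Lyft column.

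**4. Illustration with assumed counts.** The documents give no counts. Assume 10 of 116 Restylane Lyft subjects and 5 of 58 comparator subjects are medicated for a related AE. Add *m* subjects who are randomised to the comparator, given Restylane Lyft, and medicated for a related AE. These *m* are among the 58 randomised to the comparator.

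- Planned arm: 10/116 versus (5 + m)/58.
- Actual treatment: (10 + m)/(116 + m) versus 5/(58 − m).

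| m | Planned arm: Restylane Lyft vs comparator | Actual treatment: Restylane Lyft vs comparator |
|---|---|---|
| 0 | 8.6% vs 8.6% | 8.6% vs 8.6% |
| 1 | 8.6% vs 10.3% | 9.4% vs 8.8% |
| 3 | 8.6% vs 13.8% | 10.9% vs 9.1% |

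With m = 1, a 1.7-point excess for the comparator becomes a 0.6-point excess for Restylane Lyft. The sign changes because the assumed rates start equal.

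**5. The other two cases, with the same assumed 10/116.**

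- One subject treated with Restylane Lyft without randomisation, and medicated: 10/116 = 8.6% in ITT, 11/117 = 9.4% in Safety.
- Five Restylane Lyft subjects randomised but never treated: 10/116 = 8.6% in ITT, 10/111 = 9.0% in Safety. This dilution is slight.

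**The case against.** **The information is not lost.** A reader might infer that the therapy of a mis-treated or unrandomised subject disappears, or that these tables can never be reconciled with the AE tables. The SAP does not support that. Section 4 puts all subjects in the clinical database into the listings. The listings in 8.4 and 8.5 give the reason for the therapy and the related AE where one applies, and the AE listing in 10.2 gives relationship and action taken. Every record can be traced by subject. This stands, and it confines the problem to the summary tables.

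**Treatment of related AEs is already tabulated in the safety analysis.** The action-taken table in 10.2.3 falls under the as-treated rule and shows whether related AEs needed medication or other treatment. This also stands. What the 8.4 and 8.5 tables add is which drugs and procedures were given, and only that added detail is affected.

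**Mis-treatment should be rare.** Allocation is by an Interactive Response System (Protocol 5.5), subjects are randomised at the treatment visit once found eligible (8.2), the Treating Investigator is unblinded (5.6), and the products are packaged differently (5.2). SAP 9.1.3 defines exclusions for a sensitivity analysis and does not predict any number of cases. Fair, but the SAP does provide for such cases, so its safety tables should treat them consistently.

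**A subset should keep its parent's denominator.** This is a real convenience, and the change gives it up. It weighs less than keeping a safety output on the safety rule.

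**The method reference may mean layout only.** In that case the population of the two tables is unstated, and a clarifying sentence is still needed.

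**Switching will not make the tables match cell by cell.** Correct: 10.2.3 is organised by AE term and action, and 8.5 by drug class and name. The aim is the same subjects and arms, not identical cells. SAP 5.3 also does not say how to class a subject given different products at initial treatment and touch-up, and moving the tables does not settle that.

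**Conclusion.** On the natural reading of SAP 8.4 and 8.5, two descriptive safety tables use a population and arm assignment at odds with the SAP's own rule for safety data. When a subject receives the non-assigned product, therapy for that product's reaction appears under the other product. When a subject is treated but not randomised, it is absent from these tables. Untreated randomised subjects have a small diluting effect.

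The size depends on counts the documents do not give; the percentages above are illustrations at planned arm sizes. The mismatch can arise only if treatment departs from randomisation in one of the three ways that SAP 9.1.3 names. A reader might infer that any such departure must alter the tables, but that does not follow. If two subjects are swapped between arms and neither has a treated related AE, numerators and denominators are unchanged.

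No test or decision rule uses these tables. The primary analysis, type I error and power are unaffected. Low priority, but worth correcting because the correction is simple.

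**What to change.** In SAP 8.4 and 8.5, state that the additional table of procedures, and that of medications, given for treatment-related AEs will be produced in the Safety Population by actual treatment, with Safety Population denominators. Use the same as-treated classification as the AE tables, including for any subject given different products at initial treatment and touch-up. Keep the general medical history, prior and concomitant tables in ITT.

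The cost is one sentence in each of two SAP sections and a population flag in two table programs. No new data are needed. The downside is that the subset tables no longer share a denominator with their parent tables; a footnote naming the population on each would cover this.
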